9.2.1 Hematologic Improvement (HI)

Progressive disease as defined above nullifies hematologic improvement.

Erythroid response requires all of the following (only required if pretreatment HgB <11 g/dL):

- Hgb increase by ≥ 1.5 g/dL
- Relevant reduction of units of RBC transfusions by an absolute number of at least 4 RBC transfusions/8 wk compared with the pretreatment transfusion number in the previous 8 wk. Only RBC transfusions given for a Hgb of ≤ 9.0 g/dL pretreatment will count in the RBC transfusion response evaluation

Platelet response requires one of the following (only required if pretreatment platelets $< 100 \times 10^9/L$):

- Absolute increase of $\geq 30 \times 10^9/L$ (for patients starting with $> 20 \times 10^9/L$ platelets)
- Increase from $< 20 \times 10^9/L$ to $> 20 \times 10^9/L$ and absolute increase $\geq 100\%$ (for patients starting with $< 20 \times 10^9/L$)

Neutrophil response requires the following (only required if pretreatment ANC $< 1.0 \times 10^9/L$):

- At least 100% increase and an absolute increase $> 0.5 \times 10^9/L$

9.3.1 Cytogenetic Response

Complete Cytogenetic Response – Defined as reversion to a normal karyotype. For this study, reversion of a normal karyotype is defined as no clonal abnormalities detected in a minimum of 20 mitotic cells. Progressive disease as defined above nullifies cytogenetic response.

9.3 Guidelines for Evaluation of Disease

Bone marrow biopsy should be performed on Day 28 ± 4 of cycles 1, 2, 4 and 6 for clinical disease assessment. Following Cycle 6, bone marrow biopsies should be performed at the discretion of the treating physician to assess for relapse or progression.

9.4 Other Secondary Efficacy Measures

9.4.1 Treatment Failure, Overall Survival and Event-free Survival

Treatment failure is defined as failure to achieve a complete or partial remission following 4 cycles of therapy.

Overall survival is defined as the date of first dose of study drug to the date of death from any cause. Patients still alive at the time of the final analysis will be right-censored.

Event-free survival is defined as the interval from the date of first dose of study drug to date of treatment failure, recurrence, death due to any cause, or loss to follow up.

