5.2.10 Post-study Follow-up

Patients are to be followed according to standard patient care procedures for 30 days following the date of the last decitabine dose to monitor for toxicity, survival, and response. Thereafter, the investigator or designee will record information on subsequent therapy, disease progression, and/or death every 6 months for 2 years after last dose of study drug or until the patient is lost to follow-up or dies.

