5.3 Duration of Therapy

If at any time the constraints of this protocol are considered to be detrimental to the patient's health and/or the patient no longer wishes to continue protocol therapy, the protocol therapy should be discontinued and the reason(s) for discontinuation documented in the case report forms.

In the absence of treatment delays due to adverse events, treatment may continue indefinitely or until one of the following criteria applies:

- Documented and confirmed disease progression
- Death
- Adverse event(s) that, in the judgment of the investigator, may cause severe or permanent harm or which rule out continuation of study drug
- General or specific changes in the patient's condition render the patient unacceptable for further treatment in the judgment of the investigator
- Suspected pregnancy
- Serious non-compliance with the study protocol
- Lost to follow-up
- Patient withdraws consent
- Investigator removes the patient from study
- The Siteman Cancer Center decides to close the study

Patients who prematurely discontinue treatment for any reason will be followed as indicated in the study calendar.

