9.4.2 Duration of Remission and Relapse-free Survival for Patients Having Complete Remission

Duration of complete remission is defined as the interval from the date that complete remission is documented to the date of recurrence, death due to any cause, or loss to follow-up.

Relapse-free survival is defined only for those patients achieving a complete remission. It is defined as the interval from the date of first documentation of a leukemia-free state to the date of recurrence, death due to any cause, or loss to follow up.

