^h Decitabine treatment will be 20 mg/m² over a 1-hour IV infusion on consecutive Days 1-10 every 28-day cycle. The dose will be calculated based on actual patient weight at the beginning of each cycle. Patients may be premedicated with lorazepam, prochlorperazine, palonosetron, or ondansetron at the treating physician's discretion.

ⁱ Patients will be followed for 30 days following the date of the last decitabine dose to monitor for toxicity, survival and response. Thereafter, the investigator or designee will record information on subsequent therapy, disease progression, and death, every 6 months for 2 years after first dose of study drug or until the patient is lost to follow-up.

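### EFS, RFS and remission duration end at loss to follow-up with no censoring rule, EFS leaves out some AML progressions, and the length of follow-up is stated two ways

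*Combined protocol and SAP*

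**What the plan says.** The definitions are in Section 9.4, under other secondary efficacy measures.

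- **EFS (9.4.1).** "Event-free survival is defined as the interval from the date of first dose of study drug" to the "date of treatment failure, recurrence, death due to any cause, or loss to follow up".
- **Treatment failure (9.4.1).** "Treatment failure is defined as failure to achieve a complete or partial remission following 4 cycles of therapy".
- **Remission duration and RFS (9.4.2).** Both start at remission and run "to the date of recurrence, death due to any cause, or loss to follow-up" (RFS differs only in a hyphen).
- **OS (9.4.1).** First dose to death from any cause. This is the only measure with a censoring statement: "Patients still alive at the time of the final analysis will be right-censored".
- **Progression and recurrence (9.1, 9.2).** In AML, progressive disease is a category of its own, and recurrence is defined only after a complete remission. In MDS, progression and relapse share one category.
- **Stopping treatment (5.3).** One listed reason is "Documented and confirmed disease progression". Patients who stop early are then followed according to the study calendar.
- **Length of follow-up.** Section 5.2.10 says "every 6 months for 2 years after last dose of study drug", and the Section 15 data submission schedule agrees. Appendix 2, footnote i, says "every 6 months for 2 years after first dose of study drug".

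These passages say the same in every protocol version in the file.

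**The concern.** Three of the four measures put loss to follow-up in the same list as failure, recurrence and death. OS gets a sentence on censoring and the others do not, so a programmer who follows the text could code a lost patient as having had an event. That would shorten EFS, RFS and remission duration.

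EFS has a gap in the other direction. An AML patient who stops for progression after two cycles has not been assessed after four cycles and has no remission to recur from. The same holds for an AML patient who reaches partial remission and then progresses. On the literal wording, EFS for such patients continues until death or loss.

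The two follow-up rules matter most for patients treated longest. Treatment has no fixed end, and a first-dose rule uses up the 2 years while the patient is still on drug.

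The stake is the secondary efficacy reporting. Section 1.3 also plans to correlate mutation clearance with time to disease progression, which Section 9.4 does not define.

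**Working it through.** The plan gives no median, event count or power for EFS, RFS or remission duration, so it has no figure to reproduce. The check has three parts.

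**1. Losses counted as events (illustration).** The documents give no long-term loss rate, so these inputs are assumptions:

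- Event times are exponential, with 25% event-free at 24 months. The value matches the approximate 2-year survival quoted in Section 1.1, which is a survival figure and not an EFS figure.
- Loss by 24 months is 2% to 20%. The only attrition figure in the plan, 20% or less in 14.2.2, concerns availability for the molecular analysis.

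Event hazard: λ = −ln(0.25)/24 = 0.0578 per month. With losses censored, the median is ln 2/λ = 12.0 months.

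Loss hazard c solves c/(λ+c) × [1 − exp(−24(λ+c))] = proportion lost by 24 months. With losses counted as events, the median is ln 2/(λ+c), which is the true median times λ/(λ+c).

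| Lost by 24 months | Median, losses censored | Median, losses as events | λ/(λ+c) | Understated by |
|---|---|---|---|---|
| 0% | 12.0 | 12.0 | 1 | 0% |
| 2% | 12.0 | 11.7 | 0.974 | 2.6% |
| 5% | 12.0 | 11.2 | 0.935 | 6.5% |
| 10% | 12.0 | 10.5 | 0.874 | 12.6% |
| 20% | 12.0 | 9.1 | 0.761 | 23.9% |

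Check of the last row: c = 0.0578 × (1/0.761 − 1) = 0.0181. The proportion lost is then 0.239 × (1 − 0.162) = 0.200, as required. If 24-month event-free survival is varied from 10% to 40%, the understatement is 2–3% at 2% loss and 21–28% at 20% loss.

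**2. Which AML progressions are EFS events.**

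| AML patient | Treatment failure? | Recurrence? | EFS end on the literal wording |
|---|---|---|---|
| No remission after 4 cycles | Yes | No | The four-cycle assessment |
| Stops for progression before cycle 4 | Not assessed after 4 cycles | No, never in complete remission | Death or loss, or undated |
| Partial remission, then progression | No | No, never in complete remission | Death or loss |
| Complete remission, then relapse | No | Yes | Relapse |

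An assumed example is progression at the end of cycle 2 (day 56, about month 2) and death at month 6. If EFS runs to death, the patient gains 6 − 2 = 4 months. If failure is instead dated at the end of cycle 4 (4 × 28 = day 112), the gain is 112 − 56 = 56 days, or 1.8 months. The text does not say which applies.

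**3. Length of follow-up.** The two rules differ by the time from first to last dose. With 28-day cycles and ten dosing days, that is (k − 1) × 28 + 9 days for k cycles: 93 days (3.1 months) for four cycles and 149 days (4.9 months) for six. Once it exceeds 24 months, footnote i gives no six-monthly follow-up after treatment, while 5.2.10 and Section 15 give 2 years. EFS and OS still start at first dose, and RFS and remission duration still start at remission.

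**The case against.** The strongest reply is that the text never calls loss to follow-up an event. The list may only mark where observation ends, with the usual censoring taken for granted, and then there is no bias. This is a fair reading. It is not complete, because such a list would also need an end date for patients who are event-free and still followed at analysis, and none is given. The contrast with the OS sentence also invites the literal reading.

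The second reply is that a patient who stops for progression has plainly not reached remission and would naturally be called a treatment failure. That narrows the gap before cycle 4 to a missing date. It does not cover AML progression after partial remission. For MDS the gap is less clear, since recurrence may already include progression there.

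The third reply is that little depends on these measures. Section 14.2.3 only lists time to relapse and time to death, 14.2.5 explores OS in subgroups, and no analysis of EFS, RFS or remission duration is specified. This stands and limits the weight of the point.

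A reader might also infer more than the documents support:

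- **That the time-to-event results will be wrong.** This depends on losses occurring and being coded as events.
- **That the first-dose and last-dose wording gives two time origins or biases OS.** It does not. A fixed 2 years from first dose truncates follow-up administratively, and footnote i still requires 30 days after the last dose.
- **That MDS patients in Marrow CR are wrongly classed as failures.** The response rate in 14.2.3 is CR/CRi/PR, without Marrow CR, and the failure definition is consistent with that.

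**Conclusion.** The point holds as a defect in the literal definitions of secondary measures. EFS, RFS and remission duration mix loss to follow-up with true events and have no censoring rule. EFS does not count AML progression after partial remission, and it leaves AML progression before cycle 4 uncounted or undated.

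The two errors pull in opposite directions. Losses coded as events shorten the median: from 12.0 to 11.7 months at 2% loss by 24 months and to 9.1 months at 20%, with no effect if nobody is lost. These sizes rest on exponential times and assumed loss rates. Uncounted AML progressions lengthen EFS for the patients concerned.

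The follow-up contradiction is separate. It is real, and it has practical force because 5.3 sends patients who stop early to the study calendar, where footnote i sits. Under footnote i, a patient treated for more than 2 years has no six-monthly follow-up after stopping. The consequence is truncated data collection.

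The primary mutation-response analysis and the sample size are unaffected.

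**What to change.** In Section 9.4, list events and censoring separately:

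- **EFS events:** treatment failure, disease progression, recurrence or death. Progression before cycle 4 is dated when documented. State how failure is dated for patients who stop before cycle 4 for other reasons.
- **RFS and remission duration events:** recurrence or death.
- **Censoring:** patients who are lost or still event-free are censored at their last disease assessment; for OS, at the date last known alive.
- **Estimation:** Kaplan-Meier.

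Reconcile Appendix 2, footnote i, with 5.2.10 and Section 15, so that one rule governs the length of follow-up. For Marrow CR, at most state its status in EFS consistently with the response definition in 14.2.3.

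The cost is wording only, with no new assessments. Some patients move from event to censored, and some early progressors will have shorter EFS.

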9.4.2 Duration of Remission and Relapse-free Survival for Patients Having Complete Remission

Duration of complete remission is defined as the interval from the date that complete remission is documented to the date of recurrence, death due to any cause, or loss to follow-up.

Relapse-free survival is defined only for those patients achieving a complete remission. It is defined as the interval from the date of first documentation of a leukemia-free state to the date of recurrence, death due to any cause, or loss to follow up.

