9.1 Response Criteria - AML

AML Patients will be assessed for response according to the IWG criteria:¹

Morphologic complete remission (CR) – Defined as morphologic leukemia-free state, defined as less than 5% blasts in aspirate with marrow spicules and a count of ≥ 200 nucleated cells and no blasts with Auer rods or any persistence of extramedullary disease. When erythroid precursors constitute less than 50% of bone marrow nucleated cells, the percentage of blasts is based on all nucleated cells; when there are 50% or more erythroid cells, the percentage blasts should be based on the nonerythroid cells. The presence of mild megaloblastoid changes may be permitted if they are thought to be consistent with treatment effect. However, persistence of pretreatment abnormalities (eg, pseudo-Pelger-Huet cells, ringed sideroblasts, dysplastic megakaryocytes) are not consistent with CR. In addition, ANC $> 1000/\mu\text{l}$ and platelet count of $\geq 100,000/\mu\text{l}$. Patient must be independent of transfusions. No duration requirement for this designation.

Cytogenetic complete remission (CCR) – Defined as morphologic complete remission plus a reversion to a normal karyotype. For this study, reversion of a normal karyotype is defined as no clonal abnormalities detected in a minimum of 20 mitotic cells.

Morphologic complete remission with incomplete blood count recovery (CRi) – Defined as morphologic complete recovery with the exception of neutropenia $< 1000/\mu\text{l}$ or thrombocytopenia $< 100,000/\mu\text{l}$.

Partial remission (PR) – Defined as meeting the above criteria for complete remission, with the following exceptions: decrease of $\geq 50\%$ in the percentage of blast to 5-25% in the bone marrow aspirate. A value of $\leq 5\%$ blasts in bone marrow with Auer rods present may also be considered a partial remission.

Stable Disease (SD) – Defined as not meeting the definitions of CR, CRi, PR, PD, or recurrence/morphologic relapse.

Progressive disease (PD) – Defined as a clear increase in bone marrow blast count, typically a greater than 50% increase compared with baseline, or new extramedullary disease. Patients with a $> 50\%$ increase in peripheral blast count with an increase of the total peripheral white blood cell count to $> 10,000/\mu\text{l}$ should undergo evaluation by bone marrow biopsy to access for progressive disease.

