Recurrence/morphologic relapse - Defined as relapse following complete remission is defined as reappearance of blasts in the blood or the finding of $\geq 5\%$ blasts in the bone marrow, not attributable to any other cause. New dysplastic changes is considered relapse.

If there are no blasts in the peripheral blood and 5-20% blasts in the bone marrow, bone marrow biopsy should be repeated in > 1 week to confirm relapse.

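### Relapse-free survival is restricted to patients who reach complete remission but is timed from the earlier leukemia-free marrow, so if complete remission excludes CRi the wait for count recovery is guaranteed event-free time

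*Combined protocol and SAP*

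**What the plan says.** Section 9.4.2 (Duration of Remission and Relapse-free Survival) sets the analysis population: "Relapse-free survival is defined only for those patients achieving a complete remission". It then sets the start of the interval: "It is defined as the interval from the date of first documentation of a leukemia-free state to the date of recurrence". Death from any cause and loss to follow-up also end the interval. The preceding paragraph has the same end events but a different start: "Duration of complete remission is defined as the interval from the date that complete remission is documented to the date of recurrence".

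Section 9.1 (Response Criteria - AML) describes CR in two layers. The marrow layer is "Defined as morphologic leukemia-free state, defined as less than 5% blasts in aspirate with marrow spicules", with no Auer rods and no extramedullary disease. Neutrophil and platelet thresholds are then added, followed by "Patient must be independent of transfusions. No duration requirement for this designation". CRi is a separate category: "Defined as morphologic complete recovery with the exception of neutropenia" or thrombocytopenia. Recurrence is tied to a prior remission: "Defined as relapse following complete remission is defined as reappearance of blasts in the blood" or a marrow blast count at or above 5%.

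The same RFS definition appears in each protocol version in the combined document.

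**The concern.** A patient enters the RFS analysis only by reaching complete remission, but the time credited starts at an earlier date. To enter, a patient must stay alive, in follow-up and relapse-free from the clear marrow until counts recover. That stretch cannot contain an event, yet it counts as RFS. A patient who dies, is lost, or has blasts return before count recovery never enters. This is guarantee-time (immortal-time) bias, and slower count recovery makes it larger.

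The protocol foresees such a gap. Section 5.1 allows cycles to be spaced to six weeks after CRi or Marrow CR so that counts can recover, and Section 6.1 gives four cycles without adjustment for cytopenia. At stake is the interpretation of one of the secondary efficacy measures under Section 9.4.

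**Working it through.** **Reproduction.** The documents give no RFS median, rate, event count or power figure, so there is no stated number to reproduce. They also give no data on the time from marrow clearance to count recovery.

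**Identity from the definitions.** For any patient in the RFS set, the end events are the same for both measures, so

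RFS − duration of CR = date of CR − date of first leukemia-free marrow ≥ 0.

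Illustration with invented dates:
- Patient A has a clear marrow on Day 28, CR on Day 112 and relapse on Day 200. RFS is 200 − 28 = 172 days and duration of CR is 200 − 112 = 88 days. The difference of 84 days was guaranteed.
- Patient B has a clear marrow on Day 28 and blasts return on Day 100, before counts recover. Patient B is not in the RFS set.

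**Size, model 1 (assumed inputs).** Time from clear marrow to relapse or death is exponential with median m, so λ = ln 2 / m. A share f of patients would reach CR only after a wait g; the rest have no wait. A waiting patient enters only if event-free at g. Then

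S(t) = [(1 − f)·exp(−λt) + f·exp(−λg)·S_w(t)] / [(1 − f) + f·exp(−λg)],

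with S_w(t) = 1 for t ≤ g and exp(−λ(t − g)) afterwards. If everyone waits (f = 1), the median is exactly m + g and the excess is g/m.

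Excess of the as-written median over m, for m = 6, 9 and 12 months (one month = 30.4375 days):

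| Gap g | All wait (f = 1) | Half wait (f = 0.5) |
|---|---|---|
| 0 days | 0% | 0% |
| 28 days | 15%, 10%, 8% | 7%, 5%, 4% |
| 56 days | 31%, 20%, 15% | 15%, 10%, 7% |
| 84 days | 46%, 31%, 23% | 21%, 15%, 11% |

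Worked case, m = 9 months, g = 56 days (56/30.4375 = 1.84 months), f = 1:
- Median is 9 + 1.84 = 10.84 months, an excess of 20%.
- Twelve-month RFS is exp(−ln 2 × (12 − 1.84)/9) = 45.7%, against exp(−ln 2 × 12/9) = 39.7%.
- Share of patients failing before CR and so excluded is 1 − exp(−ln 2 × 1.84/9) = 13%.

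**Size, model 2 (assumed inputs).** The time model is the same, with gaps of 0, 28, 56 or 84 days equally likely. For true medians of 120, 180, 240 and 365 days, the as-written medians are 159, 220, 281 and 406 days. The excess is 33%, 22%, 17% and 11%, and the excluded share is 20%, 14%, 11% and 8%. If half the gaps are zero and the rest are split equally among the other three, the excess is 21%, 14%, 11% and 7%.

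**After alignment.** If all leukemia-free patients are counted from the leukemia-free date, or CR patients from the CR date, the guaranteed period is 0 days and the model median returns to m.

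**The case against.** The strongest reply is that complete remission in Section 9.4.2 may include CRi. The full name of CRi begins with morphologic complete remission. Section 14.2.3 pools CR and CRi as the complete response rate. Section 9.4.1 calls it treatment failure not to reach a complete or partial remission after four cycles, which would make a CRi patient a failure if CRi did not count. On that reading the qualifying date largely coincides with the leukemia-free date and the bias mostly disappears. This stands as a condition on the point. It does not remove it: Section 9.1 defines CR with count recovery and lists CRi apart, Section 9.4.2 does not mention CRi, and the exclusive reading is the more natural one. Either way the text must say which is meant.

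Four further limits stand.
- A reader might infer that RFS as defined is overstated overall. The documents do not support that. Counting loss to follow-up as an event shortens RFS, and neither model includes it.
- A reader might infer that a comparison with outside data is flattered. Section 14.2.3 plans historical comparison of response rates only, and otherwise lists time to relapse and time to death per patient. No RFS estimator, test or external comparison is specified.
- The mechanism is shown for AML only. Section 9.2 defines no leukemia-free state for MDS, so the RFS start date is unclear there.
- The gaps are assumptions. Section 5.2.6 schedules blood counts weekly at first, so recovery may be documented between marrows and gaps may be shorter than the marrow schedule suggests.

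Part of the excess also reflects a difference in population, since the comparator in the models is everyone with a clear marrow. Early failures still count in event-free and overall survival, which run from first dose.

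**Conclusion.** The point holds conditionally. If complete remission in Section 9.4.2 means CR as defined in Section 9.1, then for AML the population and the clock do not match. The interval from clear marrow to count recovery is event-free by construction, patients who fail in it are excluded, and this feature pushes RFS upward.

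The size is unknown. It is zero for patients whose marrow clearance and count recovery are documented together. Across the scenarios worked with non-zero gaps it is roughly 4% to 46% of the median: 4% to 46% in model 1 (medians of 6 to 12 months, gaps of 28 to 84 days) and 7% to 33% in model 2 (medians of 120 to 365 days, mixed gaps). These are illustrations and not bounds. They rest on exponential times and on gaps that the documents do not supply.

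The net bias in RFS is not established, because loss to follow-up as an event works the other way. The primary mutation-response analysis does not use RFS and is unaffected. It remains worth correcting before analysis, because RFS is a named secondary measure and the repair is cheap.

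**What to change.** Make the risk set and the time origin match in Section 9.4.2. Define RFS for all patients with a leukemia-free marrow (AML CR or CRi, with the corresponding MDS category named explicitly), starting at the date of that marrow. Extend the recurrence definition so that relapse counts after any of these states, since Section 9.1 now recognizes it only after complete remission. State in words whether CRi qualifies as complete remission wherever that term defines an endpoint. Keep duration of CR as the separate measure dated from CR.

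The cost is a change of wording, using dates that are already collected. The downside is that median RFS may be shorter and will include CRi patients, so the two measures need clear labels in any report.
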